### **5.5.2 Treatment Allocation**

Eligible participants infected with genotype 1 HCV will receive Zepatier treatment for 12 weeks. Zepatier contains a combination of Grazoprevir and Elbasvir. Whilst it is a licensed medication, Merck will supply GMP ready investigational medical product (IMP) for use in the trial. Those infected with genotype 3 HCV will receive commercial stock sofosbuvir off the shelf in addition to Zepatier for 8 weeks. Treatment regimens for treatment naïve and treatment experienced participants enrolled in the trial will be the same. Zepatier tablets are film-coated and each contains 50 mg Elbasvir and 100 mg Grazoprevir. Sovaldi is provided as a single 400mg tablet.

For participants in group 1, medication will be dispensed daily by the participant's community pharmacist or at the needle exchange. The pharmacist or trial nurse will observe the participant taking the medication and this will be noted in a daily log. Participants will be provided with sufficient tablets for the weekend and other days that the pharmacy/needle exchange is closed. Participants in groups 2 and 3 will fortnightly receive two week's supply of medication from the trial staff. Participants infected with Genotype 1 HCV will be instructed to take one tablet daily from the blister pack. Those infected with Genotype 3 HCV will be instructed to take one tablet daily from the blister pack and one tablet daily from the bottle. The bottle will be fitted with an electronic adherence measuring aid.

### **5.5.3 Withdrawal procedures**

Participants will be informed that they have the right to withdraw from the trial at any time without giving reasons and without prejudicing further treatment. The right to refuse to participate without reasons will be respected. After the participant has entered the trial the clinician remains free to give alternative treatment to that specified in the protocol at any stage if he/she feels that it is in the participant's best interest but, reasons for doing so will be recorded. In these cases the participants remain within the trial for the purposes of follow-up and data analysis.

Although a participant is not obliged to give reason(s) for withdrawing prematurely, if the participant appears lost to follow up, the CI will make a **reasonable** effort to ascertain the reason(s), while fully respecting the individual's rights, and will demonstrate that everything possible was done in an attempt to find any participant lost to follow-up. Those lost to follow-up or withdrawn will be identified and a descriptive analysis of them provided, including the reasons for their loss and its relationship to treatment and outcome.

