### **6.4 PARTICIPANT COMPLIANCE**

Adherence to the dosing regime is a secondary outcome of this trial. It will be checked and documented in each of the 3 arms of the trial. Those in the DOT arm will have adherence documented by the pharmacist or staff member, while those in the other two arms will be asked about adherence at each trial visit and, for participants being treated for genotype 3 HCV infection, the MEMS® caps records will be analysed. Should compliance be poor, the participant will be advised by the trial nurse or delegated individual on the importance of correct compliance. If any subject misses more than 7 consecutive doses they will be withdrawn from treatment but still followed up to the SVR 12 visit.

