### 9.2.3 Statistical analysis

Outcomes Data Analysis plan: Analysis of the trial will follow the principles outlined in the ICH E9 'Statistical Principles for Clinical Trials' and carried out by the UKCRC registered Tayside

Clinical Trials Unit (TCTU). Prior to data lock an agreed Statistical Analysis Plan (SAP) will be finalised covering the pre-specified statistical analysis.

The primary outcome of SVR will be assessed as a binary outcome for subjects and so will utilise logistic regression modelling. The numerator will be the number of subjects achieving SVR and the denominator will be total number of patients randomised to each arm. Additionally results will be expressed as a proportion of the estimated HCV infected subjects in needle exchange. The estimated number of infected patients will be based on national survey data and the empirical rate discovered in the trial (allowing for patients who refuse testing). A test of interaction between contingency and pathway will be carried out and if not significant contingency will be assessed independently. If significant then the effect of contingency will be assessed by each pathway separately. As all patients will have either achieved SVR or not and we will assume that drop-outs / lost to follow-up are failures, there will be no missing data in the primary outcome. Extra- binomial variability or over-dispersion will be examined in the logistic model and if present alternative modelling such as negative binomial models will be considered. This will also be adjusted by therapy and genotype; the two factors are interdependent determining length of therapy.

Secondary binary outcomes will be analysed in the same procedure, initially as intention to treat with all eligible patients as the denominator and then to explore the steps in the pathway by per protocol analysis in particular to analyse on treatment success:

- a) Proportion of HCV tested.
- b) Proportion who start HCV treatment within the duration of the study of those identified with HCV.

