### 9.3 MISSING DATA

The nature of this trial is to assess the applicability of this model in the real world, so incomplete data that impacts the primary outcome will be assumed to be consistent with failure of therapy and drop-outs won't be replaced. However every effort will be made to obtain missing data and as the primary outcomes are not time point critical a wide latitude for admissibility of data will be employed. We will accept measures of SVR up to 12 weeks after the due SVR12 date.

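### A sustained viral response (SVR) obtained on non-trial HCV therapy counts as a success of the allocated delivery arm, which tends to favour non-inferiority

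*Protocol*

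**What the plan says.** Protocol section 5.5.3 (Withdrawal procedures) states: "the clinician remains free to give alternative treatment to that specified in the protocol at any stage if he/she feels that it is in the" (the sentence goes on to name the interest of the participant and to require that reasons be recorded). It adds: "In these cases the participants remain within the trial for the purposes of follow-up and data analysis".

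Section 6.4 takes a participant who misses more than 7 consecutive doses off trial drug; "they will be withdrawn from treatment but still followed up to the SVR 12 visit".

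Section 9.2.3 defines the primary analysis: "The numerator will be the number of subjects achieving SVR and the denominator will be total number of patients randomised to each arm". Two rules turn a participant into a failure. Section 9.2.3 says "we will assume that drop-outs / lost to follow-up are failures", and section 9.3 says "incomplete data that impacts the primary outcome will be assumed to be consistent with failure of therapy". Section 9.3 also widens the sampling window: "We will accept measures of SVR up to 12 weeks after the due SVR 12 date".

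The Summary describes the analysis set differently (modified intention to treat, at least one dose), but that set does not remove switched participants either. The Summary justifies SVR12 as the measure of whether compliance and efficacy were sufficient within each arm. Section 9.1 sets the aim: to show that fortnightly delivery, with or without the adherence intervention, is non-inferior to directly observed therapy (DOT).

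**The concern.** Take a participant who stops the allocated course early, is given another HCV antiviral and has a negative PCR at an accepted SVR12 sample. That person was followed up and has an observed outcome, so neither failure rule clearly applies. Read as written, section 9.2.3 puts them in the numerator of the allocated arm. Yet this cure says nothing about whether that delivery method secured enough adherence, which is the Summary's reason for choosing SVR12.

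The arm with more failures has more to convert, so equal retreatment narrows a true gap. In a superiority trial that would cost power. Here it raises the chance of declaring a worse delivery method non-inferior. The per-protocol look in section 9.2.3 is described for the secondary binary outcomes, so it does not separate such cures in the primary comparison.

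**Working it through.** **Inputs from section 9.1:** DOT SVR 95%; non-inferiority limit 14 points; 5% significance (sidedness not stated); 90% power; 42 per group needed, 45 per group recruited.

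**Assumptions, not in the protocol:** a fraction r of failures on allocated therapy receives a non-trial HCV antiviral before the SVR12 sample, and a fraction c of those is then SVR. r is varied from 5% to 25% and c from 50% to 90%, the same in both arms unless stated.

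**Step 1: reproduce the plan's sample size.** With 95% in both arms and one-sided 5%:

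n = (1.645 + 1.2816)² × 2 × 0.95 × 0.05 / 0.14² = 8.565 × 0.095 / 0.0196 = 41.5, so 42 per group. This matches. One-sided 2.5% would give 51, so the plan's figure implies one-sided 5%, which is used below.

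**Step 2: place the truth at the limit.** On allocated therapy alone, DOT is 95% and fortnightly is 95 − 14 = 81%. Failures are 5% and 19%.

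**Step 3: observed rates under the protocol's scoring.**

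- DOT: 0.95 + 0.05rc
- Fortnightly: 0.81 + 0.19rc
- Gap: 0.14 − 0.14rc = 0.14(1 − rc)

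**Step 4: probability of declaring non-inferiority.** Exact binomial enumeration, 45 per arm, unpooled Wald limit, one-sided 5%:

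| r | c | DOT | Fortnightly | Gap (points) | False non-inferiority |
|---|---|---|---|---|---|
| 0 | – | 95.0% | 81.0% | 14.0 | 6.3% |
| 5% | 50% | 95.1% | 81.5% | 13.7 | 7.0% |
| 5% | 90% | 95.2% | 81.9% | 13.4 | 7.6% |
| 10% | 50% | 95.3% | 82.0% | 13.3 | 7.8% |
| 10% | 90% | 95.5% | 82.7% | 12.7 | 9.2% |
| 25% | 50% | 95.6% | 83.4% | 12.3 | 10.6% |
| 25% | 90% | 96.1% | 85.3% | 10.9 | 15.9% |

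The baseline is 6.3%, not 5%, because the Wald rule is slightly liberal at this size. That excess is not part of this point.

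**Step 5: scale in people.** A fortnightly arm of 45 at 81% has 45 × 0.19 = 8.6 failures. With r = 10% and c = 90%, 0.8 of a person is converted; with r = 25%, 1.9. One person is 1/45 = 2.2 points.

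**Step 6: when the direction changes.** With different retreatment fractions and a common cure rate, the gap is 0.14 − c(0.19 r_F − 0.05 r_D). It exceeds 14 points only if r_D/r_F is above 0.19/0.05 = 3.8. If both arms are truly 95%, equal retreatment adds 0.05rc to each and the difference stays at zero.

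**Step 7: the opposite scoring has a risk too.** Suppose one DOT participant of 45 who would have been cured switches and is scored as a failure. DOT becomes 0.95 − 1/45 = 92.8%, the gap against 81% becomes 11.8 points, and false non-inferiority is 10.7%.

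**The case against.** Several counter-arguments have weight.

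- **The rule is inferred.** No sentence says that SVR counts whatever produced it, and the term drop-out is not defined. A reader might infer that the protocol deliberately credits outside cures. It does not say so; the result follows from an unrestricted numerator combined with retention of switched participants. The SAP could add a rule, but it would have to narrow a numerator that the protocol already states.
- **Keeping switched participants is legitimate.** It is a treatment-policy approach, and retention in follow-up is not an error. What stands is that this estimand alone does not isolate the delivery method, and section 9.2.3 already treats leaving the pathway as failure.
- **Alternative treatment need not be an antiviral.** Section 5.5.3 is a general clause, and no section plans HCV retreatment before SVR12. The point applies only where the treatment is an HCV antiviral.
- **Timing limits the numbers.** Appendix 2 schedules PCR at baseline, end of treatment and SVR12 only. A relapse after end of treatment would ordinarily first appear at SVR12, where it is already a failure. The latest accepted samples are week 24 + 12 = 36 (genotype 1) and week 20 + 12 = 32 (genotype 3), so mainly early stoppers could be affected. Participants who disappear are failures anyway.
- **Direction is not assured.** DOT participants are seen daily (section 7.1), so their lapses may be noticed sooner and switching in this unblinded trial may be more frequent there. Step 7 shows that scoring switches as failures could then itself favour non-inferiority. This stands, and it is why the fix needs two analyses.

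**Conclusion.** The point holds at moderate severity. Sections 5.5.3 and 9.2.3, read together, credit an SVR on non-trial HCV therapy to the allocated arm, against the Summary's reason for using SVR12. The tendency is anti-conservative at the limit, where the type I error is defined.

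The likely size is modest: from 6.3% to about 7-9% false non-inferiority if 5-10% of failures are retreated in time, and 11-16% at 25%, which the PCR schedule makes unlikely. These figures rest on assumed retreatment and cure rates, on truth lying exactly at 95% v 81%, and on equal retreatment in both arms.

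A reader might go further and infer a severe inflation: half of all failures retreated with 90% cure gives 37.0%. Nothing in the protocol supports retreatment on that scale before the sample. Nor can one conclude that the trial will be biased in any case: truly equal arms with equal retreatment show no bias, and the gap widens if DOT failures are retreated more than 3.8 times as often.

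**What to change.** In section 9.2.3, define primary success as SVR12 achieved without any non-trial HCV antiviral between randomisation and the SVR12 sample, and score participants who received one as non-SVR. Keep them in follow-up as section 5.5.3 provides. Report SVR regardless of other therapy as a supportive analysis, tabulate switches by arm and reason, and claim non-inferiority only if both analyses support it.

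The cost is a few sentences. Concurrent medication is already recorded (section 6.6.3) and reviewed through the SVR12 visit (Appendix 2), and reasons for alternative treatment are already recorded (section 5.5.3). The downsides are a slightly lower observed SVR where switching occurs and a somewhat stricter test if the two analyses diverge; with no switches they are identical. No clinical rule changes, and the clinician's freedom to treat is untouched.

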## **6 INVESTIGATIONAL MEDICINAL PRODUCT**

### **6.1 TRIAL DRUG**

#### **6.1.1 Trial Drug Identification**

Genotype 1 infection will be treated with Zepatier (100mg Grazoprevir and 50mg of Elbasvir) supplied as one film-coated tablet to be taken once per day with or without food for 12 weeks. This is a licensed medication but the drug supplied by the manufacturer will be IMP.

Genotype 3 infection will be treated with Zepatier as above plus Sovaldi (Sofosbuvir 400mg, licensed product), taken as one film-coated tablet once daily with food for 8 weeks. The combination of Zepatier plus Sovaldi has been successfully trialled for treatment of genotype 3 hepatitis C infection (C-SWIFT and C-ISLE trials) but this combination of drugs is not licensed for treatment of HCV genotype 3 infection.

#### **6.1.2 Trial Drug Manufacturer**

Merck (Zepatier)

Gilead (Sovaldi)

#### **6.1.3 Marketing Authorisation Holder**

Zepatier is manufactured by:

Merck Sharp & Dohme Limited

[name]

[name]

United Kingdom

MA number: EU/1/16/1119/001. As stated above, the manufacturer will supply us with IMP product.

Sovaldi is manufactured by:

Gilead Sciences International Ltd

[name]

[name]

Cambridge

[name]

United Kingdom

MA number: EU/1/13/894/001 (for 1 bottle of 28 tablets) and EU/1/13/894/002 (for 3 bottles of 28 tablets).

#### **6.1.4 Labelling and Packaging**

Zepatier tablets are packaged in a carton containing two cardboard cards, each containing 2 strips of 7 sealed blisters. Participants randomised to the DOT arm will receive one tablet per day. Those randomised to the fortnightly collection of medication will receive one cardboard card, containing 2 strips of 7 blisters, making 14 blisters in total.

Participants randomised to the DOT arm will receive one Sovaldi tablet per day. Those randomised to the fortnightly collection of medication will receive one bottle containing 14 tablets every 14 days. Commercially available medication event monitoring system (MEMS®) caps will be used on the bottles of Sovaldi to enable measurement of adherence in the participants with genotype 3 infection.

#### **6.1.5 Storage**

Drugs will be stored in the Clinical Trial Pharmacy (Ninewells Hospital, Dundee). Following receipt of a prescription, a participant's drug will be dispensed from there to the community pharmacy or needle exchange centre. A drug accountability log will be held in the Clinical Trial Pharmacy. There are no special storage conditions required for either Zepatier or Sovaldi as per their Summary of Product Characteristics (SmPC).

#### **6.1.6 Reference Safety Information (RSI)**

Zepatier SmPC and Sovaldi SmPC will be held in the Trial Master File - specifically in Pharmacy Site File (PSF) and Investigator Site File (ISF). The SmPCs will be reviewed at least annually and where there have been any changes to the RSI from the SmPC version approved by MHRA, an amendment will be submitted for regulatory approval. Other changes to the SmPC will not require an amendment.

#### **6.1.7 Accountability procedures**

This will be overseen by the Clinical Trials Pharmacist in the Clinical Trials Pharmacy Department (Ninewells). This will be documented as such in the TMF and Accountability Logs will be held in the PSF.

### **6.2 DOSING REGIME**

Following randomisation, participants in the DOT group will be issued with their first dose of medication. Those with genotype 1 infection will be given one Zepatier tablet whilst those with genotype 3 will get one Zepatier tablet and one Sovaldi tablet. Participants in each of the fortnightly dosing regimens will be given two week's supply of medication. No per body weight dose adjustment is required and participants with genotype 1 will be treated for 12 weeks, those with genotype 3 for 8 weeks. 12 weeks following the end of treatment blood will be taken from

participants in order to establish whether they have achieved SVR12. Participants will be asked to consent to being followed up annually for five years to enable us to establish reinfection rates. Participants will be asked to use adequate contraception (see section 11.1).

### **6.3 DOSE CHANGES**

No dose change is planned in this trial protocol. If the participant is taken off the trial, their GP and consultant will be informed of the reason for stopping trial medication. The participant will remain in the trial for the entire duration even if the trial medications are stopped, subject to their agreement.

### **6.4 PARTICIPANT COMPLIANCE**

Adherence to the dosing regime is a secondary outcome of this trial. It will be checked and documented in each of the 3 arms of the trial. Those in the DOT arm will have adherence documented by the pharmacist or staff member, while those in the other two arms will be asked about adherence at each trial visit and, for participants being treated for genotype 3 HCV infection, the MEMS® caps records will be analysed. Should compliance be poor, the participant will be advised by the trial nurse or delegated individual on the importance of correct compliance. If any subject misses more than 7 consecutive doses they will be withdrawn from treatment but still followed up to the SVR 12 visit.

### **6.5 OVERDOSE**

Experience of human overdose with these drugs is limited. When tested in healthy volunteers, adverse reactions were similar in frequency and severity to those reported in the placebo groups.

In the event of an overdose, it is recommended that the participant be monitored for any signs/symptoms of adverse reactions and appropriate symptomatic treatment instituted.

### **6.6 OTHER MEDICATIONS**

#### **6.6.1 Permitted Medications**

Medications will be permitted as long as they do not interact with the trial drugs. The SmPC and Liverpool HEP interactions website (<http://www.hep-druginteractions.org>) will be used to identify drugs with potential interactions.

#### **6.6.2 Prohibited Medications**

Prohibited medications are those identified by the SmPC and Liverpool HEP interactions website (<http://www.hep-druginteractions.org>) as having potential interactions with the trial

drugs. GPs will be informed that their patient is participating in the study and will check compatibility prior to prescribing new drugs.

#### **6.6.3 Concomitant Medications**

Details of all concurrent medications will be recorded in the CRF.

### **7 TRIAL ASSESSMENTS**

#### **7.1 TRIAL ASSESSMENTS**

See participant trial matrix: Appendix 2

Participants who are randomised to the DOT arm of the trial will undergo daily review by their dispensing pharmacist or delegated member of staff.

Participants who are randomised to the fortnightly pick-up with psychological intervention will receive a less than one-hour individual session with a research nurse exploring their motivation and skills to adhere to their treatment regime. The intervention is described in section 3.1 and will involve a structured interview in which the trial nurse and participant will develop an action plan that includes personalised information, sources of motivation for adherence and a treatment routine configured to be compatible with the participant's lifestyle. During the intervention, participants will be guided by their trial nurse in the completion of a personalised booklet, "Hepatitis C and Me".

#### **7.2 SAFETY ASSESSMENTS**

For adverse event reporting see section 10 below.

Safety bloods to assess liver and kidney function including liver function tests (LFTs), urea and electrolytes (U&Es) Full blood count (FBC), and prothrombin time (PT) will be assessed prior to the onset of treatment to ensure that the participant can tolerate DAA therapy and at the end of treatment (week 8 for genotype 3 infection, week 12 for genotype 1 infection). LFTs will be measured at week 8 of treatment in all participants due to rare flare in alanine aminotransferase levels.

Female participants will have a urine pregnancy test prior to beginning treatment to ensure that they are not pregnant.

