#### **4.2 INCLUSION CRITERIA**

- Male or Female. (Age limit 18-70)
- HCV PCR confirmed active infection, genotype 1 or 3.
- If female, must have negative urine test results for pregnancy during initial screening period (for trial inclusion) and be advised of limited safety data in pregnancy.
- Current illicit drug use established through participant history.
- Able to provide informed consent, agreeing to trial and clinical monitoring criteria

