#### **4.3 EXCLUSION CRITERIA**

- Aggressive or violent behaviour.
- Unwilling to consent to GP being informed of their participation in the trial
- Platelet count  $< 75 \times 10^9 /l$
- Alanine transaminase  $> 350U/l$
- Inability to provide informed consent.
- Clinical history or abnormal values for albumin  $< 30 \text{ g/l}$ , Bilirubin  $> 35 \text{ umol/l}$  or PT  $> 1.5$  consistent with decompensated liver failure Childs-Pugh B or C
- Clinical history of primary hepatocellular carcinoma
- Pregnancy or breast feeding.
- Participation in a drug trial within the previous 30 days
- Hepatitis B surface antigen positive
- HIV infection.
- Hypersensitivity to elbasvir and grazoprevir
- Hypersensitivity to sofosbuvir (genotype 3 infected-participants only)
- Currently being treated with an inhibitor of organic anion transporting polypeptide 1B, e.g. rifampicin, atazanavir, daruavir, lopinavir, saquinavir, tipranavir, cobicistat or ciclosporin.
- Currently being treated with inducers of cytochrome P450 3A or P-glycoprotein, such as efavirenz, phenytoin, carbamazepine, bosentan, etravirine, modafinil or St John's Wort (*Hypericum perforatum*)
- Currently being treated with amiodarone (Participants infected with genotype 3 HCV only)

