## 5.5 RANDOMISATION

### 5.5.1 Randomisation

After successful screening for eligibility and safety, participants will be randomised to either DOT, fortnightly pick up or fortnightly pick up with psychological intervention.

PWID who are eligible for this trial have unpredictable and chaotic lives. It is therefore possible that an individual will consent to take part, provide baseline information and have blood taken for safety and eligibility checking. If eligible they may be randomised. They may then not be seen at the needle exchange for a number of weeks or even months. It is standard clinical practice that pretreatment bloods are valid for a period of 6 months and therefore we will consider baseline bloods taken for the study to be valid for 6 months unless there is a clinical indication to repeat within that period. Any clinical decision on whether bloods need to be repeated within 6 months will be made by the CI. If a consented participant reappears after a period longer than 6 months has elapsed, a documented verbal check will be made to confirm that the individual continues to consent to taking part in the study. The bloods will be re-taken and eligibility will be based on the results of these new blood tests. The blood tests taken closest to the date of treatment initiation will be considered as the baseline data. The viral genotype will not be retested as NHS lab policy is to redo this test only after 5 years have elapsed. After 6 months the baseline CRF will also be repeated to provide up-to-date pretreatment information. In this case, the information originally collected in the baseline CRF will be filed but will not be entered into the electronic data management system (Openclinica) and will not form part of the analysed dataset. To ensure that the correct, most up-to-date baseline data is entered into Openclinica, baseline data will be entered once each participant has started their treatment.

As this is an un-blinded trial, the nurse, or delegated member of staff, and participant will be aware of which arm they are allocated to. Randomisation to each of the three trial groups will be stratified by genotype so that the proportion of genotype 1 vs genotype 3 infected participants will be the same in each group. The Tayside Clinical Trials Unit (TCTU) GCP-compliant online randomisation system, TRuST, will be used by the specialist nurse or delegated, trained member of staff to perform the randomisation.

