### **8.2 DATA MANAGEMENT SYSTEM**

The data management system provided by TCTU will be OpenClinica. Development and validation of the trial database with QC and extraction of data will be done according to TCTU procedures. The DMS will be based on the protocol and case report form (CRF) for the trial and individual requirements of the investigators. The CRF will collect only information that is required to meet the aims of the trial and to ensure the eligibility and safety of the participant. The CI may delegate CRF completion but is responsible for completeness, plausibility and consistency of the CRF. Any queries will be resolved by the CI or delegated member of the trial team. The trial database will be compliant with TASC SOPs on Creating and Managing Databases. Extracts for analysis will be based on the dummy data tables provided by the trial team.

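### The urine pregnancy test is scheduled once, at baseline, with no new test at Day 0 or before a delayed first dose, although gaps of weeks or months are foreseen

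*Protocol*

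**What the plan says.** Section 7.2 of the protocol states the requirement and its purpose together: "Female participants will have a urine pregnancy test prior to beginning treatment to ensure that they are not pregnant". Section 4.3 lists "Pregnancy or breast feeding" among the exclusions.

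The timing is set elsewhere. Under section 4.2 a woman "must have negative urine test results for pregnancy during initial screening period", and section 5.3 has the test done at screening, after consent. In Appendix 2 the genotype 1 and genotype 3 matrices each mark it once, in the baseline column. Both matrices mark the inclusion and exclusion check twice, at baseline and at Day 0, and both first mark antiviral drug at Day 0.

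Section 5.5.1 deals with delay. After consent, baseline assessment and possibly randomisation, it says of participants: "They may then not be seen at the needle exchange for a number of weeks or even months". Its rule for such gaps concerns blood samples: "we will consider baseline bloods taken for the study to be valid for 6 months", unless there is a clinical reason to repeat them sooner. For longer gaps, bloods are taken again, and "After 6 months the baseline CRF will also be repeated to provide up-to-date pretreatment information".

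**The concern.** A negative urine test describes the day on which it was taken. It says nothing about conception in the weeks that follow. If the test is there to ensure that women are not pregnant when treatment begins, it has to be close to the first dose. The protocol fixes it at the far end of an interval that the protocol itself expects may run to months.

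What is at stake is exposure of a pregnancy to trial drug. The protocol treats this as something to avoid: pregnancy is an exclusion (4.3), women are to be told that safety data in pregnancy are limited (4.2), and a woman who becomes pregnant is advised to stop medication (section 11). For genotype 3 the combination is not licensed for that infection (6.1.1). The point concerns participant safety and the visit schedule. It has no bearing on the non-inferiority comparison.

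**Working it through.** The protocol has no figure of its own to reproduce here, so the check sets the schedule beside the delay rule.

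**Step 1: marks in Appendix 2 (the same in both matrices).**

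| Item | Baseline | Day 0 | Later |
|---|---|---|---|
| Urine pregnancy test | 1 | 0 | 0 |
| Inclusion/exclusion check | 1 | 1 | 0 |
| Antiviral drug administration | 0 | first mark | continues |

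The eligibility check is repeated on the day drug is first given. For the pregnancy exclusion, the only scheduled test result available to that check is the one from baseline.

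**Step 2: what section 5.5.1 renews, by length of gap between baseline and first dose.**

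- *Up to 6 months:* baseline bloods remain valid, with repeats at the chief investigator's discretion. The urine test is not mentioned, and the baseline CRF is not repeated.
- *More than 6 months:* bloods are re-taken and the baseline CRF is repeated. The urine test is not named. A new one may follow, because it is a baseline item and section 8.2 says the CRF collects what is needed "to ensure the eligibility and safety of the participant". The text does not say so.

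**Step 3: how old the negative result can be.** The protocol states no validity period for the urine test, so this has to be inferred. Nothing in the schedule renews the test before 6 months, and something might renew it afterwards. The oldest result within that window is therefore about 365 / 2 = 182 days, and 182 / 7 = 26 weeks. This is an upper limit within the window. The protocol gives no expected interval between baseline and first dose.

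**Step 4: number of added tests.** One Day 0 test per woman is needed. The protocol gives no sex split. If 20% to 40% of the 135 participants are women (an assumption), that is 135 × 0.20 = 27 to 135 × 0.40 = 54 dipsticks. The ceiling is 135, if every participant were female. These figures count tests. They do not estimate exposed pregnancies.

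**The case against.** The strongest reply is that the protocol is consistent. The test is required at screening, done at screening and marked at screening, and a screening test does come before treatment. A reader might infer that 7.2 contradicts the matrices. It does not: a baseline test satisfies the words of 7.2, and the weakness is only that the schedule does not secure the purpose given there.

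A reader might also infer that the Day 0 eligibility check has no pregnancy result behind it. That goes too far. The baseline result is on file and informs the check, and nothing forbids staff from testing again. What is true is that no new test is scheduled, so staff who follow the matrix would rely on the old result or on what the woman reports.

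A third tempting reading is that the protocol declares a pregnancy test valid for 6 months. It does not. That period is stated for bloods, and the 26-week figure is an inference from the protocol's silence on urine.

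Mitigation exists. Contraceptive advice is given to everyone, with additional contraception advised from the start of the trial (11.1), which can cover the gap before dosing. Section 11 provides for stopping drug and following the pregnancy to its outcome. These measures lower the risk and limit the consequences. But contraception is advised and not verified, 11.1 itself accepts that no method is fully reliable, and stopping acts only after exposure has been recognised. Neither measure establishes pregnancy status at first dose.

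Finally, the documents describe limited safety data and no known fetal harm, so no stronger hazard can be claimed from them.

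**Conclusion.** The point holds as a gap in the safety schedule. One urine pregnancy test is scheduled, at screening or baseline, and no new test is scheduled at Day 0 or before a delayed first dose. By inference from the blood rule and the timing of the repeated baseline CRF, a first dose may rest on a negative result up to about 6 months old. Beyond 6 months the position is unclear and may be covered.

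The conclusion assumes that staff test when the matrix tells them to and not otherwise. How many women would be affected cannot be derived, because the protocol gives neither the sex split nor the distribution of delays. Sample size, error rates and the primary analysis are unaffected. This is a cheap improvement in patient safety.

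**What to change.** Mark a urine pregnancy test at Day 0 in both Appendix 2 matrices, beside the existing inclusion/exclusion check. Add a sentence to section 7.2 requiring a negative result before medication is first dispensed. Add a rule for delay: if the first dose is not given at the Day 0 visit, trial staff repeat the test before medication is released. The rule must include release to a community pharmacy, because section 5.5.2 lets the community pharmacist dispense in the DOT arm and the protocol does not say that pharmacists can run urine tests.

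The cost is one extra dipstick per woman at a visit that already exists, using a test already in use at screening. When the first dose is delayed, a second test or an extra contact will occasionally be needed. The change is a protocol amendment and goes through the approvals in section 14.1. A narrower rule, repeating the test only after a stated interval, would save some dipsticks, but an interval would have to be chosen and tracked. A test at Day 0 for every woman is simpler to follow.
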